CLINICAL STUDY PROTOCOL

The Effect of a Group Music Therapy Advocacy Recording Intervention (MTAR) on Internalized Stigma in Adult Psychiatric Inpatients in Acute Care

10/20/2022

version 1.03

Study Personnel

PI:

[name], MT-BC Creative Art Therapist Clinical Social Services Hackensack Meridian Health Carrier Clinic [name] Office: [contact]

[contact]

Statistical support:

[name] Research Biostatistician Office of Clinical Research Administration Hackensack Meridian Health

Protocol Development support:

[name], MS, PhD Manager, Investigator Initiated Research Program HMH REDCap Administrator Office of Research Administration Hackensack Meridian Health

Abbreviations

Abbreviation	Explanation
ACU APA DSM-5	Acute Care Unit American Psychiatric Association Diagnostic and Statistical Manual of Mental Disorders (5th ed.; American Psychiatric Association, 2013)
HMHCC ISMI MT MTAR	Hackensack Meridian Health Carrier Clinic Internalized Stigma of Mental Illness Inventory Music Therapist or Music Therapy Music Therapy Advocacy Recording

Summary

The primary objective of this study is to determine the effect of a systematic music therapy intervention on internalized stigma of mental illness. The secondary objective is to evaluate the potential for the treatment effect to vary across subject diagnostic categories. This study will also examine the ability of the treatment effect to persist after 3 weeks as an exploratory objective.

Data collection will be conducted in the Acute Care Unit (ACU) of Hackensack Meridian Health Carrier Clinic (HMHCC) over a period of ten months. Subjects will be drawn from the pool of patients admitted to the HMHCC ACU during that time. Adults aged 18-65 with severe mental illness with a diagnosis of bipolar or a related disorder, depressive or anxiety disorder, or schizophrenia spectrum or other psychotic disorders as defined by the DSM-5 (5th ed.; American Psychiatric Association, 2013), of prolonged duration with a significant degree of disability or social dysfunction (Ruggeri et al., 2000) are eligible to participate. Eligible participants must be able to provide informed consent as determined by the doctor.

1 – Introduction

This study will be investigating the effects of the Music Therapy Advocacy Recording intervention (MTAR) on internalized stigma in adult inpatients in acute psychiatric care. MTAR is a sequence of group music therapy songwriting and recording sessions framed as a mental health awareness project to be shared with the general public. Internalized stigma is the subjective, nonconscious process of assimilating socially transmitted stereotypes and negative messages about mental illness into one's own belief system (Corrigan, 2005; Link, 2001; VandenBos, 2007). It is distinct from direct experiences and perceptions of social stigma (Corrigan, 2005; Hinshaw, 2009). Internalized stigma is negatively associated with quality of life (Degnan et al., 2021; Picco et al., 2016), self-esteem (Lysaker et al., 2008; Segalovich et al., 2013), recovery orientation (Yanos et al., 2008), morale (Ritsher & Phelan, 2004), social adaptation (Firat, 2020; Link, 1987; Lysaker et al., 2007; Perlick et al., 2001), general functioning (Yanos et al., 2012; Muñoz et al., 2011), symptom severity (Corrigan, 2004; Livingston & Boyd, 2010; Lysaker, 2010; Tesfaye, 2020), treatment adherence (Fung et al., 2009), and medication adherence (Semahegn et al., 2021), and it is positively associated with delayed treatment seeking (Fox et al., 2018; Sirey et al., 2001; Tucker et al., 2013; Vogel et al., 2013; Wade et al., 2015) and greater risk of suicide (Schomerus et al., 2015). Considering the scope and gravity of related outcomes, developing treatment strategies for internalized stigma has naturally become a topic of considerable interest in current mental health research.

Five recently published meta-analyses and systematic reviews (Alonso et al., 2019; Büchter & Messer, 2017; Tsang et al., 2016; Wood et al, 2016; Yanos et al., 2015) have drawn mixed conclusions about the efficacy of interventions designed to address internalized stigma. Tsang et al. (2016) assert that "most internalized stigma reduction programs appear to be effective", while Büchter & Messer (2017), "did not find any encouraging results". Authors' conclusions and recommendations for optimal intervention development and approach are similarly varied. Alonso et al. (2019) posit that psychoeducation and interventions combining elements of psychoeducational, cognitive-behavioral, narrative, motivational, peer support, and empowerment strategies showed the best results. Wood et al. (2016) recommend that interventions target specific demographics, while Tsang et al. (2016) call for more innovation. For Büchter & Messer (2017), the most important aspects of developing new approaches are systematic literature review and involvement with people from stigmatized groups. The wide array of recommendations from these authors highlights the need for more research in this area, including the need for new evidence-based interventions to address internalized stigma.

None of these systematic reviews and meta-analyses evaluate music therapy approaches. Music therapy is currently used in a wide range of mental health settings with diverse and varied populations (Eyre, 2013). Recent Cochrane reviews of music therapy and depression (Aalbers et al., 2017) and schizophrenia (Geretsegger et al., 2017) found that music therapy can improve functioning and quality of life, and reduce depressive and anxiety symptoms in patients with depression and schizophrenia. Sparse but promising research has suggested the potential efficacy of music therapy for addressing internalized stigma (Silverman, 2013; Woofenden, 2020) with songwriting, improvisation, and community performance-based methods. The intervention designed for this study combines elements of these methods in a way that is informed by the music therapy literature, and expands upon these approaches with the added component of a music therapy recording session aimed at creating music for mental health awareness.

Though a rich precedent exists for utilizing recording technology in music therapy, its clinical potential and therapeutic relevance have not been systematically investigated. Kirkland & Nesbitt (2019) offer a model of therapy-oriented recording as a medium for self-reflection and personal narrative review for patients with concurrent psychiatric disorders. When framed as a mental health advocacy project to be released to the general public, recording the patient-composed song in the MTAR treatment sequence offers patients an opportunity to proactively work together in a socially supportive context to change public perception of mental illness, to refute self-relevance of stereotypes by strengthening and broadening self-concept, and empower themselves and each other with creative, expressive tools to confront and adapt to the "experience, perception, or anticipation of negative social reactions" (Livingston & Boyd, 2010) to mental illness that initiate stigma internalization.

In this study, subjects will work together with a certified music therapist (MT) in groups of 5 to 7 subjects per group to compose, rehearse, and record a song to be released to the general public for the purpose of generating anti-stigma mental health awareness. The primary objective is to reduce internalized stigma from baseline relative to the control group as measured by the 29-item Internalized Stigma of Mental Illness Inventory (ISMI; Ritsher et al., 2003). The secondary objective, examining the association between treatment effect and diagnostic category, can assist in generating hypotheses related to effective implementation. The exploratory goal of the study is to examine the potential for the treatment effect of the music therapy intervention to persist after 21 days from baseline.

The mechanism of change in this study is rooted in the aesthetic decision-making intrinsic to the musical experiences of songwriting, active music-making, and music recording. In making these decisions, subjects integrate symbolic representations of the lived experience of stigma into a healthy and expanded self-concept. This process is aided by the mutual social support in collaborating on the artistic product, transforming the negative experiences and perceptions of social stigma into an object of beauty and a catalyst for social change. The recording also serves as a post-treatment reminder of the subject's successful attainment of a meaningful goal and their agency to effect positive change.

2 - Background

2.1. Background/literature review

There is substantial literature examining the processes related to stigma internalization and approaches to address it. The impact of internalized stigma upon a person's recovery is connected to how they make sense of their subjective experience and diagnosis of mental illness in the context of widely-held beliefs (Yanos et al., 2010). The "Illness Identity" model (Lysaker et al., 2007; Yanos et al., 2008, 2010, & 2020) describes how internalized stigma precipitates poor outcomes via the "insight paradox" (Lysaker et al., 2007) which posits that the interaction between stigma internalization and increased awareness of one's mental illness results in increased hopelessness and decreased self-esteem. Hopelessness and low self-esteem contribute to increased avoidant coping, leading to increased risk of suicide, social interaction, and vocational functioning, which can amplify symptom severity (Lysaker et al., 2007; Yanos et al., 2008, 2010, 2020).

Recent meta-analyses offer insight into theoretical foundations of programs seeking to address internalized stigma. Degnan et al (2021) conclude that "psychological interventions should target improvements in [self-concept and social networking] to reduce the negative impact of stigma on quality of life in psychosis". Yanos et al. (2015) assert that "tools and experiences designed to increase or elicit hope, empowerment, and motivation to act toward one's goals and according to one's values" are important components of interventions aimed at reducing internalized stigma. In alignment with these recommendations, this music therapy approach offers subjects opportunities to expand self-concept by highlighting their innate aesthetic sensibilities as expressed in the creative process, provides tools to engage in self-advocacy which can transform "illness identity" into an empowered self-concept, and utilizes the intrinsic motivation of musical experiences to instill hope in the accomplishment of

a specific goal. The collaborative group format provides opportunities for participants to build social skills that can be used to strengthen post-treatment support networks.

Drapalski et al. (2013) identify four clinical "pathways" intended for use as a basis for developing interventions targeted at reducing internalized stigma. The MTAR intervention utilizes each of the four in a distinct phase: Songwriting and Arrangement, Rehearsal, Recording, and Review (see Table 1).

Clinical "pathway", Drapalski et al. (2013)	Related MTAR phase(s)	Description of MTAR phase
Undermine the perceived accuracy and self-relevance of stereotypes	Verbal Processing; Songwriting and Arrangement	Confront and refute stereotypes by sharing personal perspectives and experiences of stigma in lyric writing.
Reinforce the inaccuracy of stereotypes by broadening self-concept	Rehearsal	Build a sense of competence and mastery rooted in intrinsic musicality, aesthetic sensibility, and creative expression.
Realistically assess rejection probability	Recording	Experience acceptance, social support, and group cohesion in the face of potential judgment and rejection; access vulnerability by making musical decisions based on personal aesthetic.
Connect with non-stigmatizing others	Editing and Review	Work together to achieve a sense of pride and connectedness in accomplishing a goal; connect with others in the pursuit of betterment on intrapersonal, interpersonal, and societal levels.

Table 1. Phases of MTAR treatment sequence as related to Drapalski et al.'s (2013) model

Narrative enhancement approaches are also common in interventions that address internalized stigma (Alonso, 2019; Roe et al., 2010; Yanos et al., 2012). These approaches utilize cognitive restructuring techniques (Beck, 1970) to challenge maladaptive beliefs by developing self-affirming personal narratives. This study does not utilize narrative enhancement or cognitive restructuring per se, but draws from and expands on these techniques conceptually. By centering an advocacy project on a shared group narrative in the context of aesthetic expression, the intervention offers participants opportunities to reframe their life histories from a self-affirming perspective, and to substantiate the reframing with a new experience that can build self-efficacy and a sense of mastery (Schulze, 2009), and nurture a sense of connectedness to a larger whole.

Yanos et al. (Yanos et al., 2010) suggest group advocacy work as a potential treatment for internalized stigma, and highlight the efforts of mental health consumer advocacy and self-help groups to aid mental illness recovery by empowering identity transformation. Qualitative evidence suggests that the "mental health consumer" approach can help patients integrate negative experiences into a healthy self-concept through self-disclosure combined with advocacy work (McCoy et al., 1994; Onken & Slaten, 2000). The potential for these programs to increase resistance to stigma internalization, while promising, has not been systematically studied. The proposed study draws from the self-disclosure and self-advocacy elements of the mental health consumer movement, but it is not peer-led or a self-help group. The music therapist-led format was selected because the typically higher acuity of

hospitalized subjects necessitates a consistent and coherent procedure with skilled facilitation to contain and ground the work.

Of recently developed interventions included in meta-analyses and systematic reviews that demonstrated a significant reduction of internalized stigma, the intervention most similar to the current study is Photovoice (Russinova et al., 2014). Photovoice is a peer-based photography intervention combined with psychoeducation, personal narrative construction, and community activism. Like MTAR, Photovoice aligns with Drapalski et al.'s (2013) and Degnan et al.'s (2021) recommendations for intervention development, and incorporates the identity transformation work of the mental health consumer movement (Yanos et al., 2010) by working in groups to create an artistic product aimed at effecting social change. The core principle of both MTAR and Photovoice is to integrate negative memories of stigmatizing experiences into an empowered narrative, which is then realized as an aesthetic artifact and transmitted to a wide audience as an agent of social change. However, MTAR differs from Russinova et al.'s (2014) study in a number of significant ways (see Table 2).

Though MTAR is grounded in the research literature related to internalized stigma treatment, there are two notable divergences. First, nearly all published studies included in meta-analyses examine interventions that take place as part of outpatient treatment. While outpatient approaches may be less complicated to implement and measure, they are often remedial of internalizing stigmatizing experiences related to inpatient hospitalization. MTAR is implemented during inpatient treatment, at the critical juncture when the internalization of experiences related to hospitalization is nascent. Second, most interventions include psychoeducation as a fundamental component. Psychiatric inpatients, who typically present with a higher acuity level and may be psychotic or actively decompensating, can lack the insight for significant reflexive thinking, and can rarely self-regulate to the degree required to sit for a 60- or 90-minute psychoeducation class. For this reason, psychoeducation in this study is limited to a 10-minute introduction to the concept of internalized stigma in the first session of the treatment sequence.

A major benefit of addressing internalized stigma in an inpatient setting with music therapy is that musical experiences are intrinsically motivating and pleasurable. This stands in contrast with much of the inpatient psychiatric hospital experience, which is often characterized by isolation (Lindgren et al., 2019), feeling unsafe (Berg et al., 2017), powerlessness related to a perceived lack of influence on choice of medication and treatment (Færden et al., 2020), and feeling bored or "caged in" (Stewart et al., 2015). Music therapy is a non-threatening opportunity to take part in new experiences with new people. Combined with the acquired awareness of internalized stigma in the presence of social support, engaging in new experiences can strengthen participants' resistance to stigmatization by building internal resources based on the need for novel experiences (Szcześniak et al., 2018).

In a peer-reviewed music therapy study that provides quantitative data that demonstrates a reduction in internalized stigma in an inpatient psychiatric setting, Silverman (2013) examines the effects of a songwriting intervention in which subjects compose lyrics for "The Stigma Blues". The study concluded that music therapy was significantly more effective in addressing internalized stigma relative to the control group, and the author suggests that the songwriting

Photovoice (Russinova et al., 2014) Characteristic	MTAR Characteristic	Rationale of Divergence
Narrow diversity of demographic characteristics in study sample/small sample size	Broad diversity of demographic characteristics at HMHCC; larger sample size	Greater generalizability of research findings

One-dimensional mode of creative expression (photography)	Multiple modes of creative expression: lyric-writing, composing, performing, and recording music.	Engaging in creative expression in various aesthetic modes offers opportunities to adapt to changing and evolving moods, perspectives, and feelings in real-time.
Parallel creative process	Collaborative creative process	Collaborating on a single work of art, rather than multiple individual works, requires a greater investment in social interaction.
Collection of individual narratives	Individual narratives integrated into a group narrative	Building a group narrative creates more opportunities for group cohesion
Peer-led	Music therapist as facilitator	MT can guide, contain, ground the sessions for higher-acuity inpatients; create meaningful opportunities by interfacing between patient and technology; occupy a supportive role in realizing group aesthetic
Outpatient	Inpatient	Prompt intervention to improve outcomes

Table 2. Comparison of Photovoice (Russinova et al., 2014) and MTAR Characteristics and Rationale of Divergence

process contributed to a disinhibition of self-disclosing personal histories of stigmatizing experiences (Silverman, 2013). MTAR includes a songwriting component, but also expands upon Silverman's approach (See Table 3).

The use of recording technology to address internalized stigma is a novel approach. A qualitative music therapy study based on a community music therapy approach (Solli & Rolvsjord, 2015) which included recording, mixing, and producing music, subjects emphasized that music therapy "represented freedom from illness, stigma, and treatment". This suggests that a music therapy recording session can provide a locus for transforming a participant's illness identity. Using recording technology creates the opportunity to utilize the public relations and social media infrastructure of the hospital to to promulgate the work as part of a mental health awareness project. Participants' belief in their potential to effect large-scale societal change via musical expression of their personal experiences is the central mechanism for instilling feelings of empowerment and motivation in this study.

"The Stigma Blues" (Silverman, 2013) Characteristic	MTAR Characteristic	Rationale of Divergence
Single-session intervention	Four-phase treatment sequence over five sessions	Build trust, group cohesion, engagement with the musical process
Blues format	Open musical format	Broad scope of musical

		expression
No advocacy component	Advocacy-based	Identity transformation through empowerment
MT performs the music	Subjects rehearse and perform the music	Identity transformation through competence and mastery
No recording component	Includes Recording and Review Phases	Extend treatment effect by monumentalizing the work for reflection and insight
Demographic data (diagnosis) not collected	Demographic data (diagnosis) collected	Investigate potential relationships between treatment effect and diagnoses to inform future developments and implementation

Table 3. Comparison of "The Stigma Blues" (Silverman, 2013) and MTAR Characteristics and Clinical Rationale of Divergence

Using recording technology creates a record of subjects' achievement that can be accessed at any time in the future and serve as a post-inpatient treatment reinforcement of an empowered identity, potentially extending the treatment effect. MTAR's actual capacity to induce systemic change is out of scope for this study.

The proposed study fills the gap between Photovoice (Russinova et al., 2014), the mental health consumer movement (McCoy et al., 1994; Onken & Slaten, 2000), and the music therapy research of Silverman (2013) and Solli & Rolvsjord (2015) with an inpatient treatment sequence that combines elements of artistic collaboration to bolster self-esteem, self-concept, and social support; and community activism building a sense of agency, self-efficacy, and empowerment. It will focus on how the music therapy group, in nurturing expressive and aesthetic modes-of-being centered on mental health advocacy in the context of peer support, can diminish or prevent internalized stigma.

3 - Rationale, Objectives and Hypothesis

3.1. Study Rationale/Problem Statement/Research question or Study significance

What are the effects of a music therapy intervention focused on writing, recording, and releasing music to the general public for the purpose of mental health advocacy on internalized stigma of mental illness among adult inpatients in acute care?

3.2. Hypothesis

Adult psychiatric inpatients on an acute care unit who participate in music therapy groups focused on writing, recording, and releasing music to the general public for the purpose of mental health advocacy will report less internalized stigma from baseline relative to the control group upon completion of the treatment sequence, regardless of subject diagnosis. The effect will persist when measured at 3-weeks post-baseline.

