3.6. Secondary Outcome Variable

ISMI score pre-treatment, ISMI score post-treatment, ISMI score 3 weeks post-treatment, Diagnostic Category: No Diagnosis, Diagnostic Category: Schizophrenia Spectrum and Other Psychotic Disorders, Diagnostic Category: Bipolar and Related Disorders, Diagnostic Category: Depressive Disorders, and Diagnostic Category: Anxiety Disorders

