5.8. Statistical Method

5.8.1. Sample size calculation and justification

Based on power analysis (power=80%, see assumptions below) and the design of the study, 50 patients will be accrued to each group (n=100).

The study has a two-factor repeated-measures ANO VA design. For the power analysis, the assumption of sphericity will be made (*epsilon* = 1). Sphericity is the condition where the variances of the differences between all combinations of related groups (levels) are equal.

Assumptions and parameters of power analysis:

Sphericity: *epsilon* = 1 Type I error: *alpha* = 0.05 Type II error: *beta* = 0.2

Required power: power = 100(1 - B) = 80%Effect size: f = 0.1, 0.25, 0.33, 0.4, 0.8

Cohen's effect size for F test, 0.1 ("small"), 0.25 ("medium"), 0.33, and 0.4 ("large"). Effect

size of 0.33 was used.

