5.8.2. Statistical Analysis Plan

Primary Analysis

Treatment effect on the primary dependent variable (ISMI score) will be measured by using a two-factor repeated-measures analysis of variance (ANOVA). A P value of less than 0.05 will be considered to indicate statistical significance.

Secondary Analysis

Treatment effect on the secondary dependent variables (diagnosis category) will be measured by using a two-factor repeated-measures analysis of variance (ANOVA). A P value of less than 0.05 will be considered to indicate statistical significance.

Exploratory Analysis

Treatment effect on the exploratory variable (ISMI score 3 weeks after baseline) will be measured by using a two-factor repeated-measures analysis of variance (ANOVA). A P value of less than 0.05 will be considered to indicate statistical significance.

6 - Trial Administration

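### Section 3.2 hypothesises benefit whatever the diagnosis, but the planned secondary analysis has no treatment-by-diagnosis term or other criterion that could support it

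*Combined protocol and SAP*

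**What the plan says.** Section 3.2 hypothesises less internalized stigma "relative to the control group upon completion of the treatment sequence, regardless of subject diagnosis". Section 3.5 sets the secondary objective as a reduction across diagnostic categories and lists five, one of them for patients without a diagnosis.

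The Summary puts the question differently: "The secondary objective is to evaluate the potential for the treatment effect to vary across subject diagnostic categories". Section 1 says that this work "can assist in generating hypotheses related to effective implementation". Table 3 also presents the diagnosis data as a way to inform later development.

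The analysis is one sentence in section 5.8.2: "Treatment effect on the secondary dependent variables (diagnosis category) will be measured by using a two-factor repeated-measures analysis of variance (ANOVA"). The criterion follows: "A P value of less than 0.05 will be considered to indicate statistical significance". No treatment-by-diagnosis term, confidence-interval criterion or margin is named. Section 5.8.1 justifies 50 patients per group for one overall comparison ("Based on power analysis (power=80%, see assumptions below"), with the effect size fixed by "size of 0.33 was used" (Cohen's f). It gives no power or sample size by category.

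**The concern.** The same question appears as a hypothesis to be confirmed in 3.2 and as an open, hypothesis-generating one in the Summary and Introduction. Section 5.8.2 does not settle which it is.

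In a two-factor repeated-measures ANOVA, the two factors are naturally arm and time, which leaves no place for diagnosis. If diagnosis replaces arm, the model no longer contains the treatment. Diagnosis is a baseline characteristic, so it cannot be the outcome either. As written, the analysis does not estimate how the treatment effect differs by diagnosis.

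Naming the interaction would not be enough by itself. A significant interaction would show that the effects differ. A non-significant one would leave open whether every category benefits. With nothing else specified, that second result could be misread as confirming 3.2, and a diagnostic group that gains nothing could be reported as benefiting.

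**Working it through.** **Inputs from the documents.** 50 per arm, 100 in total; alpha 0.05; f = 0.33 (5.8.1). Five categories are listed in 3.5, 3.6 and Appendix 1. The Summary requires a listed diagnosis for entry, so the no-diagnosis category may be empty (four categories), and it can be read as joining depressive with anxiety disorders (three). ISMI test-retest reliability is 0.68 to 0.92 (4.3).

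**Assumptions, not in the documents.** Equal categories balanced between arms, independent patients, no dropout. For two equal arms d = 2f = 2 × 0.33 = 0.66 SD. The scenario is an effect of 0.66 SD in every category but one, and zero in that one.

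**Step 1: the plan's own figure.** A two-group F test has noncentrality f² × N. At f = 0.33, 80% power needs N = 76, and N = 100 gives 90%. Repeated-measures versions with two arms need fewer than 76. The stated 100 is therefore not reproduced from the inputs given. That is a separate matter; what counts here is that the figure concerns the overall comparison only.

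**Step 2: interaction power, 0.66 in SDs of the analysed score.** With n per arm per category and k categories, noncentrality = (n/2) × Σ(effect − mean effect)², with k − 1 and 100 − 2k degrees of freedom.

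| Categories | n per arm | Noncentrality | df | Power |
|---|---|---|---|---|
| 3 | 16.67 | 8.33 × 0.2904 = 2.42 | 2, 94 | 26% |
| 4 | 12.5 | 6.25 × 0.3267 = 2.04 | 3, 92 | 19% |
| 5 | 10 | 5 × 0.3485 = 1.74 | 4, 90 | 15% |

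Unequal categories can lower this. With a 40/30/20/10 split and no effect in the smallest, power is 11%.

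**Step 3: precision, same scale.** With four categories, the 95% CI half-width for one category's effect is 1.96 × √(2/12.5) = 0.78 SD, wider than the assumed effect of 0.66. For a difference between two category effects it is 1.96 × √(4/12.5) = 1.11 SD (0.96 with three categories, 1.24 with five).

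**Step 4: sensitivity to the pre-post correlation.** The plan does not say which SD its effect size refers to. If 0.66 is in raw-score SDs and change is analysed, the SD of change is √(2(1 − r)), and the four-category noncentrality becomes 2.04 / (2(1 − r)).

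| r | SD of change | Noncentrality | Power | CI half-width, difference of two effects (raw SD) |
|---|---|---|---|---|
| 0.68 | 0.80 | 3.19 | 28% | 0.89 |
| 0.80 | 0.63 | 5.10 | 43% | 0.70 |
| 0.92 | 0.40 | 12.76 | 85% | 0.44 |

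**The case against.** The documents already frame the question as exploratory in the Summary, section 1 and Table 3, and it is not inconsistent to expect benefit across diagnoses while looking for variation. The clause in 3.2 could mean only a pooled effect in a diagnostically mixed sample. This has weight: the defect is a mismatch between 3.2 and the rest, not a plan committed throughout to a confirmatory claim. But the pooled reading does not remove the need for a secondary analysis that contains both treatment and diagnosis.

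A reader might infer more than the documents support:

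- **That a non-significant result will be declared proof of equal effects.** Section 5.8.2 has no rule for P above 0.05. The misreading is a risk that nothing in the plan blocks; it is not a stated intention. Benefit in every category is also weaker than equal effects, because effects may differ in size and all still be beneficial.
- **That tests will be run within small cells of a known size.** No diagnostic mix is given and no separate within-category tests are specified. The 12.5 per arm above is an assumption, and an interaction test would use all patients.
- **That the trial could never detect variation.** At r = 0.92 on the raw-score scale, four-category power is 85%. That is the top of the cited reliability range and looks optimistic for acute inpatients over about a week, but it cannot be excluded. Good power would still not turn a non-significant result into evidence of benefit in each diagnosis.

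**Conclusion.** The concern holds in this limited form: the planned secondary analysis could not support the diagnosis clause of 3.2, because it names no treatment-by-diagnosis term and no criterion for benefit by category. This follows from the text and depends on no numerical assumption.

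The numbers show how little a non-significant interaction would usually mean. Under equal categories, independent patients and one category without effect, power is 15% to 26% on the analysed-score scale. On the raw-score change scale with four categories it is 28% to 85% across the cited reliability range. Uneven categories, patients dropped under section 5.2, or dependence within wings could make matters worse. The primary comparison is not affected.

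**What to change.** - **Section 3.2:** delete the closing clause about diagnosis from the statement of benefit.
- **Section 3.5:** restate the objective as estimating the treatment effect by diagnostic category.
- **Section 5.8.2, Secondary Analysis:** replace the two-factor P<0.05 rule by a model with the treatment-by-diagnosis (by time) term. Report each category's treatment effect and the between-category differences with 95% CIs, labelled hypothesis-generating as in section 1. State that a non-significant interaction will not be reported as evidence of benefit in all diagnoses, or of equal effect across them.

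The cost is protocol and analysis-plan wording, with no extra patients or data. The downside is that the trial gives up any claim of uniform benefit.

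Separately, section 3.6 includes the 3-week score among the secondary variables ("ISMI score pre-treatment, ISMI score post-treatment, ISMI score 3 weeks post-treatment, Diagnostic Category: No Diagnosis"), while 3.8 lists it as exploratory. The two sections should be reconciled.
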